# **Primary end point:**

Calculating time to intubate (TTI) which is defined as time duration from loss of twitch to confirmation of end tidal CO 2. Comparing time to intubate (TTI) between study and control group using a t-test to compare means.

Non-inferiority margin set at 15 seconds. Non- inferiority hypothesis (H  $_0$ : Mean TTI diff  $\geq$ 15 s, H  $_A$ : Mean TTI diff < 15 s).

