R 3.5.3 software will be used for statistical analysis.

Non-Inferiority Study Design

Hypothesis

Use of the barrier box prolongs the mean TTI by more than 15 s compared to a control group with no barrier box

HO: Mean TTI changes with barrier box

HA: Mean TTI does not change with barrier box

Non-inferiority margin: Our research team decided to use 15 s as non-inferiority margin. The premise of our non-inferiority study is to compare the mean TTI and infer if the additional time taken for airway manipulation with a barrier box is within acceptable non-inferiority margin between the means of both the groups (Box vs No Box). Non-inferiority margin of 15 s is considered acceptable while comparing airway manipulation in both the groups based on our clinical experience and pilot study data. Our literature review showed that this non-inferiority margin ($\Delta = 15$ s) would be within safe period of apnea tolerated by most patients (Moon et.al.)

Baseline data

Descriptive statistics for baseline demographics will include:

- Age in years- mean (standard deviation)
- BMI mean (standard deviation)
- Sex (male or female) frequency, number of participants
- American Society of Anesthesiology (ASA) Physical Status frequency, number of participants. ASA Physical Status is a classification system to assess a patient's preanesthesia medical co-morbidities, and helps predict perioperative risk when used with other risk factors such as frailty, level of deconditioning and type of surgery.
 - \circ ASA 1 a normal healthy patient
 - \circ ASA 2 a patient with mild systemic disease
 - ASA 3 A patient with severe systemic disease
 - The study will exclude patients who are ASA 4 (a patient with severe systemic disease that is a constant threat to life) or ASA 5 (a moribund patient who is not expected to survive without the operation).

Continuous variables of age and body mass index (BMI) will be reported as mean and standard deviation. Categorical variables of Gender (Sex) and ASA Physical Status will be reported in frequency tables.

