For continuous variables, the two groups ("barrier box" or "no barrier box") will be compared using unpaired two-sample t-tests, if data meets assumptions for normally distributed data within each group and homogeneity of variances (equal variance between groups) For categorical variables, the two groups ("barrier box" or "no barrier box") at baseline will be compared using chi-square test of independence.

Primary endpoint

The primary end point is time to intubate (TTI) in seconds, from loss of twitch to confirmation of end tidal carbon dioxide.

TTI will be collected by an independent provider (registered nurse) not directly involved in airway management. The TTI is used as an outcome measure as it is an objective variable that can be measured and helps us in assessment of airway manipulation with a barrier box. We plan to use objective end points to eliminate inter- observer variability.

For the primary endpoint, mean TTI and 95% confidence intervals will be assessed and compared in the two groups, "barrier box" and control with "no barrier box".

An unpaired two-sample single-sided t-test will be used to test our non- inferiority hypothesis. The TTI of the barrier box group is expected to be higher than the mean TTI of control the group. Analysis will include two independent sample comparison of means using one sided t-test in R.

The t-test will be done based on assumptions that the sample has no dependence between subjects in the control group and the barrier box group. Similar variance in both the groups will be confirmed by Levine's test. With the sample size > 30, samples are expected to be from a population with a normal distribution. Results will be considered statistically significant when p < 0.05.

If the difference of the mean TTI between the groups is less than the non-inferiority margin of 15seconds, then the null hypothesis will be rejected.

Secondary endpoints and statistical analysis include:

- Attempts at intubation
 - o assessed as frequency (percentage) of patients intubated on first attempt.
- Need for bag mask ventilation (yes or no) during induction, defined as the time taken from propofol bolus to loss of twitches measured with a peripheral nerve stimulator.
 - assessed as frequency (number) of patients.
- Lowest oxygen saturation during induction (Lowest peripheral capillary oxygen saturation during induction, defined as the time taken from propofol bolus to loss of twitches measured with a peripheral nerve stimulator.

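### The SAP's primary decision rule does not say that the one-sided t-test is against 15 s, and read literally it lets the observed mean difference alone decide non-inferiority

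*SAP*

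**What the plan says.** **Protocol, Primary end point (statistical analysis plan section).** The margin is 15 s. The null is a mean TTI difference of 15 s or more and the alternative is "Mean TTI diff < 15 s". The analysis is described only as a t-test comparing means, with no sidedness, null value or confidence bound.

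**SAP, Non-Inferiority Study Design, Hypothesis.** The opening line reads "Use of the barrier box prolongs the mean TTI by more than 15 s compared to a control group with no barrier box". The labelled hypotheses follow: "HO: Mean TTI changes with barrier box" and "HA: Mean TTI does not change with barrier box". The 15 s margin is then justified by clinical experience, pilot data and tolerated apnea time.

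**SAP, Primary endpoint.** The test is stated as "An unpaired two-sample single-sided t-test will be used to test our non- inferiority hypothesis", and TTI is expected to be longer with the box. The level is given as "Results will be considered statistically significant when p < 0.05". For intervals, "mean TTI and 95% confidence intervals will be assessed and compared in the two groups". The closing decision sentence is that if "the difference of the mean TTI between the groups is less than the non-inferiority margin of 15seconds, then the null hypothesis will be rejected".

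**The concern.** Three parts of the SAP should describe the same criterion, and they do not.

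- **Hypotheses.** The labelled null and alternative have neither margin nor direction. Under that null, faster intubation with the box counts as a change and so belongs to the null. The alternative is a statement of no difference, which a one-sided test cannot establish. Rejecting the protocol's null supports only a delay of less than 15 s. The opening hypothesis line does name 15 s, but it states what the protocol treats as the null.
- **Test.** A one-sided t-test is named without the value it tests against. The only directional cue nearby is that the box group should be slower. An analyst could therefore run a test against zero in the greater direction, which asks whether the box is slower and not whether it is non-inferior.
- **Decision.** The final sentence compares the difference in means with 15 s. It mentions no p-value or confidence limit and no order of subtraction. The planned 95% intervals are described for mean TTI in the two groups, and no interval for the difference is specified.

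At stake is the primary conclusion. If the final sentence is applied as written, sampling error plays no part in it and the 5% level stated just before it is not controlled.

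**Working it through.** **Inputs from the documents.** Margin 15 s (protocol and SAP). One-sided t-test, p < 0.05 (SAP, Primary endpoint). Sample size: 10 s difference, two-sided 5%, 80% power, 36 per group, 20% dropout, 45 per group enrolled (Sample size calculation, both documents). No SD of TTI is given.

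**The plan's own figure.** 36 / (1 − 0.20) = 45 per group, 90 in total, which reproduces. The 36 cannot be checked directly without an SD. Solving the two-sample t-test power equation (noncentral t, 36 per group, 10 s, two-sided 5%, 80%) backwards gives SD = 14.93 s. I use this as an assumption, with an assumed range of 10 to 30 s.

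**Standard error of the difference.** SE = SD × √(2/n). At SD 14.93 s this is 3.52 s (n = 36) and 3.15 s (n = 45).

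**Reading A, literal rule (pass if the observed difference is below 15 s).** P(pass) = Φ((15 − true difference)/SE).
- True difference 15 s: Φ(0) = 0.50 for any SD and any n.
- True difference 17 s: Φ(−2/3.52) = 0.285 (n = 36); Φ(−2/3.15) = 0.263 (n = 45).

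**Reading B, one-sided 5% t-test of H0: difference ≥ 15 s.** It passes if the observed difference is below 15 − t(0.95, 2n − 2) × SE.
- n = 36: 15 − 1.667 × 3.52 = 9.1 s.
- n = 45: 15 − 1.662 × 3.15 = 9.8 s.
- P(pass) at a true 15 s is 0.05 by construction. At 17 s it comes from the noncentral t distribution.

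| | n | SD 10 s | SD 14.93 s | SD 30 s |
|---|---|---|---|---|
| Largest passing observed difference, test | 36 | 11.1 s | 9.1 s | 3.2 s |
| | 45 | 11.5 s | 9.8 s | 4.5 s |
| P(pass) at true 15 s, literal / test | either | 50% / 5% | 50% / 5% | 50% / 5% |
| P(pass) at true 17 s, literal / test | 36 | 20% / 0.7% | 28% / 1.4% | 39% / 2.7% |
| | 45 | 17% / 0.5% | 26% / 1.1% | 38% / 2.5% |

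Simulation at a true 15 s (200,000 runs for each combination of SD 10, 15 and 30 s with 36 and 45 per group) gave 0.499 to 0.501 for the literal rule and 0.050 for the test.

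**Example.** An observed difference of 12 s with 45 per group and SD 14.93 s satisfies the literal rule. Against 15 s, t = (12 − 15)/3.15 = −0.95 and one-sided p = 0.17 (0.08 to 0.32 over SD 10 to 30 s). The same data pass under one reading and fail under the other.

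**How often the readings part.** At the plan's own 10 s difference, 45 per group and SD 14.93 s, the literal rule passes 94% of the time and the test 47%. Every pass on the test is also a pass on the literal rule, so they disagree in about 94 − 47 = 47% of such trials.

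**The case against.** The strongest reply is that the decision sentence is shorthand. It follows directly after a one-sided test of the non-inferiority hypothesis and a significance level, and rejecting a null is the language of a test. The protocol supplies the 15 s null, nothing in the SAP withdraws it, and box minus control is the natural direction. On that view there is one coherent analysis, poorly drafted, and the 50% figure describes a rule nobody meant to use.

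That reading is possible and may well be what was intended. But no sentence in the SAP states it, and the SAP's own labelled hypotheses and its expectation of a slower box group point away from it. The protocol does not settle the matter either, because its t-test has no stated null value.

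Parts of the objection stand. Direction can be inferred from context. The missing interval for the difference would not alone make the criterion inconsistent. Only the 50% versus 5% contrast is free of the assumed SD. The low power at a true 10 s comes from sizing the trial for a two-sided 10 s difference, which is a separate matter. Finally, the SAP is dated November 2024 and the documents do not say whether data were already in hand, so the timing of any correction matters.

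**Conclusion.** The concern holds, and the text must be fixed because this is the rule that decides the trial. The SAP's hypotheses contradict the protocol's, its test lacks a null value, and its decision sentence can be met by the point estimate alone. Under the literal reading the false non-inferiority rate at the margin is 50% instead of 5%, with no assumption about SD or sample size.

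The width of the disputed zone does depend on the SD. At the back-solved 14.9 s, observed differences from about 9.1 s (36 per group) or 9.8 s (45 per group) up to 15 s would be called non-inferior by one reading and not by the other. Over an SD of 10 to 30 s the lower end of that zone runs from 11.1 down to 3.2 s (36) or from 11.5 down to 4.5 s (45).

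**What to change.** 1. Replace the SAP's labelled hypotheses with the protocol's, adding direction. H0: mean(box) − mean(control) ≥ 15 s. HA: mean(box) − mean(control) < 15 s. Reword the opening hypothesis line to agree.
2. Delete the decision sentence or replace it with: *Non-inferiority is concluded only if the one-sided two-sample t-test with null value 15 s gives p < 0.05, equivalently if the upper limit of the two-sided 90% confidence interval for the difference in mean TTI (box minus control, same variance option) is below 15 s.*
3. State the R call: box as the first group, `mu = 15`, `alternative = 'less'`.
4. Report that interval for the difference alongside the group means.

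This keeps the sponsor's margin, test and level. A one-sided 0.025 level, matching a 95% interval, is a stricter option but is not needed to reconcile the text.

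**Cost.** Wording only, with no new data. If outcome data had already been seen, the change should be dated and disclosed. The criterion is stricter than the literal rule, so power should be stated (one-sided 5%, SD assumed):

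| True difference | n | SD 10 s | SD 14.93 s | SD 30 s |
|---|---|---|---|---|
| 0 s | 36 | >99% | 99.5% | 68% |
| | 45 | >99% | 99.9% | 76% |
| 10 s | 36 | 68% | 41% | 17% |
| | 45 | 76% | 47% | 20% |

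At the optional 0.025 level, power at a true 10 s and SD 14.93 s is 29% (36 per group) or 35% (45 per group).

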## **Study end points:**

Primary end point:

Calculating time to intubate (TTI) which is defined as time duration from loss of twitch to confirmation of end tidal CO 2.

Secondary end point:

- 1)Time duration from induction with propofol to confirmation of endotracheal tube
- 2) Need for bag mask ventilation and duration of ventilation
- 3)Episode of hypoxia as evidenced of Spo2 < 90 %
- 4) Subjective assessment of intubation by provider: easy /moderate /difficult

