 - assessed as mean and standard deviation
- Induction time defined as the time taken from propofol bolus to loss of twitches measured with a peripheral nerve stimulator.
 - o assessed as mean (in seconds) and 95% confidence intervals

For continuous variables, the two groups ("barrier box" or "no barrier box") will be compared using unpaired two-sample t-tests, if data meets assumptions for normally distributed data within each group and homogeneity of variances (equal variance between groups)

For categorical variable, the two groups ("barrier box" or "no barrier box") will be compared using chi-square test of independence.

Airway assessment data will be collected for the two groups ("barrier box" or "no barrier box") as frequency data (number of patients) and will include:

- Mallampati score (scale of 0 to 4) used to assess and prepare for possible difficult intubation of participants who score high. Lower scores are less likely to have a difficult intubation, and higher scores are more likely to have a difficult intubation.
- Number of patients will be assessed in both groups for each of these classes:
 - Mallampati 0 (Any part of the epiglottis is visible)
 - Mallampati 1 (soft palate, uvula, and pillars are visible)
 - Mallampati 2 (soft palate and uvula are visible)
 - Mallampati 3 (only the soft palate and base of the uvula are visible)
 - Mallampati 4 (only the hard palate is visible)
- Thyromental Distance (TMD) > 3 finger breadth
 - TMD is the distance from the thyroid notch to the chin when the head is extended. TMD is used to assess and prepare for possible difficult intubation of participants who are less than or equal to 3 finger breadth. A distance of greater than 3 finger breadth may be less likely to have a difficult airway or airway constriction

Number of patients with TMD > 3 finger breadth will be assessed in both groups

- Inter incisor distance > 3 finger breadth
 - Inter incisor distance is the distance between the upper and lower teeth of the open mouth of a patient. Inter incisor distance is used to assess and prepare for possible difficult intubation of participants who are less than or equal to 3 finger breadth. A distance greater than 3 finger breadth may be less likely to have a difficult airway or airway constriction

Number of patients with Inter incisor distance > 3 finger breadth will be assessed in both groups.

- Neck range of motion (Full or Restricted)

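### The SAP stops measuring oxygen saturation and bag-mask ventilation at loss of twitches, where time to intubate begins, and omits the protocol's SpO2 < 90% and bag-mask duration endpoints

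*SAP*

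**What the plan says.** **SAP, Primary endpoint.** "The primary end point is time to intubate (TTI) in seconds, from loss of twitch to confirmation of end tidal carbon dioxide".

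**SAP, Secondary endpoints.** Four outcomes are listed: first-attempt intubation, bag-mask need, lowest saturation and induction time. Three share one window:
- Bag-mask need: "Need for bag mask ventilation (yes or no) during induction, defined as the time taken from propofol bolus to loss of twitches".
- Lowest saturation: "Lowest peripheral capillary oxygen saturation during induction, defined as the time taken from propofol bolus to loss of twitches", which is to be "assessed as mean and standard deviation".
- Induction time: "Induction time defined as the time taken from propofol bolus to loss of twitches measured with a peripheral nerve stimulator".

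**Protocol, Study end points.** The secondary endpoints include these, the first two with no time window:
- "Episode of hypoxia as evidenced of Spo2 < 90" (per cent).
- "Need for bag mask ventilation and duration of ventilation".
- "Time duration from induction with propofol to confirmation of endotracheal tube".

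**Protocol, Routine procedures for all patients.** Hypoxia and the duration of bag-mask ventilation appear again as data points. Induction time is defined here from the loss of spontaneous breathing to tube placement, which differs from the SAP. The section also foresees further intubation attempts and removal of the box if it causes difficulty.

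**The concern.** The protocol's Background says TTI is being studied to show that the box can be used safely. The SAP's Non-Inferiority Study Design section defends the 15 s margin partly on the ground that most patients tolerate that much apnea. Any extra time in TTI is spent between loss of twitch and end-tidal CO2. Whether patients tolerated it would show in saturation and mask ventilation during that phase.

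Read literally, the SAP leaves a desaturation during laryngoscopy, or mask ventilation between attempts, out of every specified analysis. The trial could then report reassuring oxygenation results that exclude the phase on which the margin's justification rests.

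**Working it through.** The plan gives no figure on this point, so the check is mainly a comparison of windows and endpoint lists.

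**1. Windows**

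| Outcome (SAP) | Starts | Ends |
|---|---|---|
| Bag-mask need | propofol bolus | loss of twitches |
| Lowest SpO2 | propofol bolus | loss of twitches |
| Induction time | propofol bolus | loss of twitches |
| TTI | loss of twitch | end-tidal CO2 confirmation |

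The first three end where TTI begins, so the overlap is nil. First-attempt intubation also covers the TTI phase, but it and TTI measure success and speed, not oxygenation or ventilation. The early window is still relevant to the box: under Procedures involved in Human research, the patient's head is positioned in it before induction. The gap is therefore limited to loss of twitch through end-tidal CO2.

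**2. Endpoint lists**

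| Protocol secondary endpoint | In the SAP list? |
|---|---|
| Propofol to confirmed tube | No; replaced by propofol to loss of twitches |
| Bag-mask need | Yes, but ends at loss of twitches |
| Bag-mask duration | No |
| SpO2 < 90% episode | No; replaced by lowest SpO2, mean and SD, ending at loss of twitches |
| Provider-rated difficulty | No |

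A mean and SD of lowest SpO2 do not give the number of patients below 90%, even inside the SAP window.

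**3. Recovering the protocol's time endpoint**

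If tube confirmation means end-tidal CO2, then for each patient:

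(propofol to loss of twitches) + (loss of twitch to end-tidal CO2) = propofol to confirmed tube.

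That is SAP induction time plus TTI, so no new measurement is needed.

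**4. What a restored SpO2 < 90% endpoint could show**

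*Arm sizes.* These are 36, or 45 after the 20% dropout allowance in the sample size section: 36 / (1 − 0.20) = 45, which reproduces the plan's figure.

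*Event counts.* The documents give none, so those below are assumptions.

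*Zero episodes in an arm.* The exact (Clopper-Pearson) 95% upper limit is 1 − 0.025^(1/n):
- n = 45: 7.87%
- n = 36: 9.74%

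*Difference, box minus control.* The Newcombe 95% interval takes the Wilson limits (l, u) of each arm. With d = p1 − p2:
- lower limit = d − √[(p1 − l1)² + (u2 − p2)²]
- upper limit = d + √[(u1 − p1)² + (p2 − l2)²]

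For 3 vs 0 at 45 per arm, p1 = 6.67% (Wilson 2.29% to 17.86%) and p2 = 0% (0% to 7.87%):
- lower = 6.67 − √(4.37² + 7.87²) = −2.3
- upper = 6.67 + 11.19 = 17.9

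| Assumed episodes | 45 per arm | 36 per arm |
|---|---|---|
| 0 vs 0 | 0 (−7.9 to 7.9) points | 0 (−9.6 to 9.6) points |
| 3 vs 0 | 6.7 (−2.3 to 17.9) points | 8.3 (−2.7 to 21.8) points |

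**The case against.** **The protocol endpoints were never withdrawn.** The SAP introduces its list with a word that need not be exhaustive. The protocol's confidentiality section promises descriptive statistics for the objectives, and the data sheet records hypoxia and bag-mask need with no window. It is fair to say these data may still be summarised. But none of these places specifies an analysis of the omitted endpoints or changes the SAP's stated windows. Data collected without a planned analysis are part of the problem.

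**Bag-mask need is a proxy for desaturation.** Under Routine procedures for all patients, ventilation after induction is withheld unless SpO2 falls below 90%. If that is followed, a bag-mask yes inside the SAP window signals a desaturation, and the rule may explain the choice of window. This stands as a partial answer before loss of twitch. It does nothing for the phase after it.

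**The trial is small and its patients selected for lower risk.** This is true. The exclusions cover ASA 4 and 5, severe cardiopulmonary compromise, BMI above 35 and anticipated difficult airway, and the intervals above are wide. They describe the precision of the remedy, not the size of the gap. This argues for an estimate with an interval, not for leaving the phase out.

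**Only secondary reporting is affected.** The primary test is indeed untouched, and the propofol-to-tube time is a minor loss because its mean follows from two outcomes already analysed. The oxygenation gap cannot be recovered that way.

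**Conclusion.** The concern holds. Two SAP windows end exactly where TTI begins, and two protocol endpoints that could have covered the later phase, SpO2 < 90% and bag-mask duration, are not in the SAP list. No oxygenation or ventilation endpoint specified in the SAP therefore covers loss of twitch to end-tidal CO2.

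This conclusion rests on the wording of the windows and lists, not on the illustrative counts. The number of events that would be missed cannot be estimated from the documents. The primary TTI comparison stands. What lacks support as planned is any statement that the added time was tolerated. This should be fixed, and confidence is high.

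**What to change.** In the SAP:

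1. Extend the measurement window for lowest SpO2 and for bag-mask ventilation to end-tidal CO2 confirmation.
2. Restore the SpO2 < 90% episode: number and percentage per arm, with a 95% interval for the difference (for example Newcombe). Present it as an estimate, not a test of safety.
3. Restore bag-mask duration.
4. Report propofol bolus to tube confirmation as the protocol's secondary time. Propofol to loss of twitches can stay as a descriptive time.
5. Reconcile the two definitions of induction time. In the same pass, state whether provider-rated difficulty is still a secondary endpoint.

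**Cost.** Mostly SAP wording. SpO2 < 90% and bag-mask need already have data sheet fields. Lowest SpO2 and bag-mask duration do not, so they may need re-extraction from the electronic record; the documents do not say whether it holds time-stamped values that allow this. The SAP is dated November 2024, and the protocol planned a four-month study in 2020. If data were already collected, the change must be disclosed as made after collection. Clinical care and the primary analysis do not change.
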